9.2 Predetermined Covariates and Prognostic Factors and other Analyzed Factors

The following factors will be adjusted for as covariates and used in the analysis models as fixed effect:

- Treatment sequence, which has two levels: nabiximols/placebo (coded as 1) and placebo/nabiximols (coded as 2),
- Treatment period, which has two levels: Period 1 (coded as 1) and Period 2 (coded as 2),
- Baseline / Period baseline (as continuous covariates)

9.3 Analysis Sets

9.3.1 Treatment Arm

The “**as randomized**” **treatment arm** is defined as the treatment allocated at each treatment period according to the randomization scheme.

The “**as treated**” **treatment arm also** called “actual treatment arm” is defined as the treatment received for the longest period of time within each treatment period.

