#### **5.3.4      Investigational Medicinal Product Accountability**

The investigator has overall responsibility for the accountability of all used and unused IMP. A drug accountability record for the IMPs must be kept current and must contain the following:

- Trial code
- Batch number/packaging reference number, date of receipt, and quantity of IMP received
- Patient's trial identification number
- Date and quantity of IMP dispensed
- The initials of the dispensing/dosing party
- Date and quantity of IMP returned to the investigator
- IMP expiry dates

The IMP will be dispensed at Visits 2, 4, 6, and 8. Patients will be asked to return all IMP (used and unused) at each subsequent visit (Visits 4, 5, 8, and 9). The trial site will check the returned IMP against the usage recorded in the electronic diary. Any discrepancies will be discussed with the patient at the time of the visit and documented accordingly within the patient's source documents.

The investigator must inform GW promptly of all missing or unaccounted IMP.

A record of returned IMP must be completed and included in the shipment of used and unused IMP to the relevant drug distribution depot. At the end of the trial, a record/statement of reconciliation must be completed and provided to GW.

These inventories must be made available for inspection by an authorized GW representative and local officials or regulatory agency inspectors.

Please refer to the separate pharmacy manual for more detailed information on the IMP.

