9.3.2.4 Safety Analysis Set

All patients from the Screening Analysis Set, who received at least 1 dose of IMP in the trial will be included in the Safety Analysis Set and analysed according to the treatment received. Only patients for whom it has been confirmed that they did not take IMP will be excluded from the Safety Analysis Set. The Safety Analysis Set will be used to report all safety data using the actual treatment arm.

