12.4 Important Protocol Deviations

All important protocol deviations (IPDs) are defined in a study specific protocol deviation guidance and classified as presented in Appendix 1 Classification of Protocol Deviations. The IPDs that are determined to affect the primary efficacy results will be classified as major IPDs as reported Appendix 1 Classification of Protocol Deviations. The occurrence of major IPDs will identify which patients maybe excluded from PP Analysis Set.

IPDs linked to COVID-19 will be identified. Patients for which at least one IPD has been identified, will be listed along with their deviation reason; demographics and treatment sequence for inclusion in the clinical study report (CSR) based on the deviation data will be entered into the clinical trial management system (CTMS).

The study team and the Sponsor will conduct ongoing reviews of the deviation data from both an internal system of record named Predictive Study Operations (PSO) and any other additional major IPDs that were missed and now identified through SAS programming of the blinded ADaM datasets, and the resulting set of evaluable patients throughout the study, adjusting the deviation criteria as seems appropriate. The PP Analysis Set must be finalized at the post-freeze data review meeting (or earlier), prior to database lock and unblinding. However, in case a patient is receiving a treatment kit he/she is not allocated to, this will be considered as a major IPD before unblinding but the impact on the PP Analysis Set will only be determined following unblinding. This particular case will clearly be identified prior to database lock.

Based on the Randomized Analysis Set, the number and percentage of patients with important protocol deviations by category, as well as the number and percentage of patient with IPDs linked to COVID-19, by category, will be summarized by treatment sequence and overall.

Based on the FAS, the number and percentage of patients with at least one major IPD and the number and percentage of patients with major IPDs linked to COVID-19 will also be summarized by treatment sequence and overall.

Using the Randomized Analysis Set and the Safety Analysis Set (if deemed necessary to account for any patients exposed out of randomization) IPDs will be listed by treatment sequence and patient identifier and flagged for belonging to FAS and Safety Analysis Set. In this listing major IPDs, and IPDs linked to COVID-19 will be identified.

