12.7.1 Adverse Events

Adverse events (AEs) will be coded using MedDRA 24.0 or higher according to the version in use at time of database lock. All safety analyses of AEs will be performed by actual treatment arm and reported using the Safety Analysis Set. An AE will be considered a TEAE if it first occurs or worsens in severity or seriousness after the first dose of IMP intake and before the last dose date + 15 days.

All AEs will be classified during the pre-treatment period, the 51-day safety on-treatment period or during the follow-up period as follows:

Events that occurred before first IMP intake without worsening or becoming serious after the first IMP dose are classified as **pre-treatment AEs**;

Events that occurred or worsens between first IMP dose and 14 days after IMP last dose are classified as on-treatment AE and are defined as **treatment-emergent AEs** (TEAEs);

- TEAE occurring during 21-day on-treatment safety Period 1 will be considered emergent to actual treatment received during Period 1 (as defined in [Section 10.1.1](#)).
- TEAE occurring during 21-day on-treatment safety Period 2 will be considered emergent to actual treatment received during Period 2 (as defined in [Section 10.1.1](#)).

Events occurring more than 15 days after last dose are classified as **follow-up AEs**.

Consequently, TEAEs will be summarized by treatment arm using the actual treatment received at each given period. Any adverse event occurring during the wash-out period will be linked to the actual treatment arm defined for Period 1, whereas any AEs occurring after last IMP dose will be linked to the actual arm defined at time of permanent study drug discontinuation.

The following events will not be identified as AEs in this study:

- Medical or surgical procedures (e.g., surgery, endoscopy, tooth extraction, etc.). The condition (the “triggering event”) that leads to the procedure are adverse events and will be reported as such.

- Pre-existing conditions present or detected prior to the first dose of study drug that do not worsen during the study.

Counting rules

For incidence reporting, if a patient reported more than one AE that was coded to the same preferred term/system organ class within a given treatment arm, the patient will be counted only once for that specific preferred term/system organ class by treatment arm and the rules defined below will be applied.

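### After a wrong-treatment kit at an in-window Visit 4 or 8, the longest-received rule tabulates adverse events on the second drug under the drug no longer being taken

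*SAP*

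**What the plan says.** SAP 9.3.1 defines two arms. The as-randomized arm follows the randomization scheme. The as-treated or actual arm "is defined as the treatment received for the longest period of time within each treatment period". SAP 9.3.2.4 then states: "The Safety Analysis Set will be used to report all safety data using the actual treatment arm".

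SAP 12.7.1 applies that label to adverse events by period, not by the drug taken at onset: "TEAE occurring during 21-day on-treatment safety Period 1 will be considered emergent to actual treatment received during Period 1", with matching wording for Period 2. It also says "Any adverse event occurring during the wash-out period will be linked to the actual treatment arm defined for Period 1", and "any AEs occurring after last IMP dose will be linked to the actual arm defined at time of permanent study drug discontinuation". The at-risk count in the same section requires at least one spray, but within the actual arm.

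On supply, Protocol 5.3.4 says: "The IMP will be dispensed at Visits 2, 4, 6, and 8". It asks patients to return all IMP at Visits 4, 5, 8 and 9. Each period therefore has two kits used one after the other.

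The SAP foresees a wrong-treatment kit. Appendix 1 lists it as major deviation 13, and section 12.4 says that "in case a patient is receiving a treatment kit he/she is not allocated to, this will be considered as a major IPD before unblinding". The only consequence stated there concerns the Per Protocol set.

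Two other passages use a different principle. The Safety Analysis Set in Protocol 13.3 is analyzed by treatment received, with no longest-time rule. SAP 12.7.5.3 assigns C-SSRS data by the first and last intake dates of each drug.

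**The concern.** Without a kit error, the actual and randomized arms coincide and the longest-received rule does nothing. It matters only when a period contains both drugs, and there it gives the whole period to one of them. If the second kit is the wrong one, adverse events that begin while the patient takes that drug are counted under the drug already stopped and returned. In a placebo period with nabiximols supplied at Visit 4 or 8, nabiximols events enter the placebo column; the opposite error puts placebo events under nabiximols. If the first kit is the wrong one, the whole period takes the wrong drug's label, and events on the correct second kit follow it.

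The tables concerned are still to be produced. Section 7.0 of the SAP addendum cuts back the efficacy and pharmacokinetic work but keeps the safety reporting as set out in the SAP, to support the safety assessment of a marketed product.

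**Working it through.** **Inputs.** Visit days and windows come from Protocol 9.1.2.3, 9.1.4.1, 9.1.4.3 and Appendix 1: Visit 4 on Day 15 ±1, Visit 5 on Day 21 ±2, Visit 6 on Day 31 ±1, Visit 8 on Day 45 ±1, Visit 9 on Day 51 ±2.

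**Formulas.** First kit = day of re-supply − day of first dose in the period. Second kit = day of last visit − day of re-supply + 1. The whole switch day is credited to the second kit, which favors it.

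**Plan's own figures.** The protocol gives about 14 days of titration and 7 of maintenance. Period 1: 15 − 1 = 14 and 21 − 15 + 1 = 7. Period 2: 45 − 31 = 14 and 51 − 45 + 1 = 7. Both agree.

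**All in-window combinations.**

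| | First kit (days) | Second kit (days) | Combinations | Second kit longer |
|---|---|---|---|---|
| Period 1 | 14 − 1 = 13 to 16 − 1 = 15 | 19 − 16 + 1 = 4 to 23 − 14 + 1 = 10 | 3 × 5 = 15 | 0 |
| Period 2 | 44 − 32 = 12 to 46 − 30 = 16 | 49 − 46 + 1 = 4 to 53 − 44 + 1 = 10 | 3 × 3 × 5 = 45 | 0 |

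The closest case is 12 against 10 days (Visit 6 on Day 32, Visit 8 on Day 44, Visit 9 on Day 53). There are no ties.

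**When the result would reverse.** With Visit 5 on Day 21, Visit 4 would have to fall on Day 11 or earlier (21 − 11 + 1 = 11 against 11 − 1 = 10). With Visit 5 on Day 23, it would have to fall on Day 12 or earlier (12 against 11). If only dosing days count, a titration pause of 8 days would do it on the nominal schedule (14 − 8 = 6 against 7).

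**Data affected per patient.**
- Adverse events after a Visit 4 error: Safety Period 1 runs through washout (SAP 10.1.1 and 12.7.1), so Days 15 to 30 are affected: 30 − 15 + 1 = 16 of 30 days.
- Adverse events after a Visit 8 error: Days 45 to 51, plus up to 14 days after the last dose, although routine recording ends at Visit 10 (nominally Day 58).
- Laboratory tests and ECG: the only scheduled on-treatment assessment in each period is at Visit 5 or 9 (SAP 12.7.3 and 12.7.5.2), on the second kit. All of that period's scheduled on-treatment data are affected.
- Vital signs: the Visit 5 or 9 measurement.
- C-SSRS: not affected (SAP 12.7.5.3).

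**Weight of one patient.** One misassigned patient can move the incidence of a term in an arm by 1/190 = 0.53 percentage points at the planned size, or 1/170 = 0.59 at 170. Enrollment stopped before the planned number was reached, so the weight is larger in practice. The documents do not give the final number.

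**The case against.** The strongest objection is carry-over. The SAP treats events up to 14 days after the last dose as treatment-emergent, and the whole second-kit interval of 4-10 days falls inside that span. If nabiximols was taken first and placebo was wrongly supplied at Visit 4, attribution by kit in use would move late or withdrawal effects of nabiximols to placebo, whereas the present rule keeps them under nabiximols. This stands as a cost, and neither rule is perfect for a mixed period. It does not rescue the present rule, because the SAP already accepts the same switch between periods. Nominally Period 2 starts 31 − 21 = 10 days after the last Period 1 dose, and events from Day 31 go to the new drug although the 14-day window runs to Day 35.

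The IRT names each pack, and section 12.4 treats the error only as a contingency. Cases are also traceable: wrong kits are listed as deviations, all adverse events are listed with start dates, and deaths get narratives. A reader might infer that nabiximols events would be hidden. The listings do not support that; only the summary tables would be wrong.

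A reader might also infer that all safety data are misassigned, or that a wrong second kit can never become the label. The first fails because C-SSRS has its own rule and liver elevations after permanent discontinuation go to the last treatment received (SAP 12.7.3.1). The second fails because Protocol 8.1.2 allows pauses in titration, Protocol 9 allows visit windows to be extended, and Appendix 1 of the SAP foresees visits out of window.

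**Conclusion.** The point holds for mixed-kit periods with in-window visits and uninterrupted dosing. A wrong-treatment kit at Visit 4 or 8 cannot change the actual arm, so treatment-emergent events that start on the second drug, and the Visit 5 or 9 laboratory, vital-sign and ECG data, are tabulated under the drug not being taken. A wrong first kit gives the mirror error.

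Per affected patient the effect is substantial: about 16 of 30 days of adverse-event attribution after a Visit 4 error, and all scheduled on-treatment laboratory and ECG data of the period. A reader might reduce this to 7 of 21 days, or one third of the safety data. That fraction leaves out washout and does not describe assessments made once per period.

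The effect on the trial as a whole is unknown. The documents give no kit-error rate, it may be zero, and they do not support any assumed count of patients. Efficacy is not involved, because it is analyzed by randomized treatment. The change is worth making because it is cheap, fits the protocol's treatment-received principle, and touches tables that the addendum retains.

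**What to change.** Amend SAP 9.3.1, 9.3.2.4 and 12.7.1 before unblinding, for periods with a wrong-treatment kit only:

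- Assign each treatment-emergent event and safety assessment to the drug of the kit in use at onset or assessment, from IRT records and dispensing dates. The SAP already works this way for C-SSRS and at the switch to Period 2.
- Count the patient at risk under each drug of which at least one spray was taken in that period.
- Keep the longest-received label only for period-level summaries that need a single arm.
- State a rule for events on the switch day. Both kits may be used that day, and adverse-event onset is recorded as a date.
- Footnote or list mixed-kit periods, and flag events that start within 14 days of the last dose of the earlier drug. On the nominal schedule, with the last first-kit dose on Day 14, the flag runs to Day 28. It therefore covers the whole second-kit interval and most of the washout.

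The cost is a few lines of SAP text and a merge with the kit list after unblinding. A patient with a mixed period counts under both drugs in that period, and some events carried over from the first drug may be attributed to the second, which is why the flag is needed. Periods without a kit error do not change.

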9.3.2 Definition of Analysis Sets

9.3.2.1 Screening Analysis Set

All patients who signed the inform consent and have performed Visit 1 (screening).

9.3.2.2 Randomized Analysis Set

All patients who signed the informed consent and were randomized by IRT will be included and analysed according to their randomized treatment arm / treatment sequence.

9.3.2.3 Full Analysis Set

All patients who signed the informed consent and are randomized and received at least 1 dose of IMP in the trial, will be included and analyzed according to their randomized treatment. The Full Analysis Set is the primary analysis set for all efficacy endpoints and patient reported outcome (PRO) assessment.

9.3.2.4 Safety Analysis Set

All patients from the Screening Analysis Set, who received at least 1 dose of IMP in the trial will be included in the Safety Analysis Set and analysed according to the treatment received. Only patients for whom it has been confirmed that they did not take IMP will be excluded from the Safety Analysis Set. The Safety Analysis Set will be used to report all safety data using the actual treatment arm.

9.3.2.5 Study Completer Analysis Set

All patients from the FAS who have completed the trial (completed both treatment period 1 and treatment period 2), regardless whether they have permanently withdrawn from study drug. The analyses on the Study Completer Analysis Set will only be conducted on efficacy endpoints and patients analyzed according to their randomized treatment arm.

9.3.2.6 Per Protocol Analysis Set

The Per Protocol (PP) Analysis Set is defined as follows: a subset of the FAS that includes all patients who have completed the trial with no major important protocol deviations deemed to compromise the assessment of efficacy. Major important protocol deviations will be identified as a subset of the important protocol deviations and fully defined prior to unblinding of the trial. The PP analysis will only be conducted on efficacy endpoints and patients analyzed according to their randomized treatment arm.

9.3.2.7 Pharmacokinetic Analysis Set

All patients who have received at least 1 dose of IMP and provided sufficient bioanalytical data to calculate reliable (based on the judgement of the pharmacokineticist) estimates of the PK parameters of THC, CBD, and their metabolites will be included in the PK Analysis Set. This analysis set cannot be determined before unblinded analysis.

10.0 Conventions and Derivations

10.1 Study Period, Reference Day, Study Day, Analysis Day and Visit Window

10.1.1 Study Periods

For each patient, there will be a screening period, an evaluable period composed of a treatment period 1, a washout period, and a treatment period 2, and a safety follow-up period.

The Screening period starts on the day of the informed consent signature and ends on Day 1 (as defined on in [Section 10.1.2](#)) before 1st IMP intake.

The evaluable period starts on the day of randomization and ends the day of the safety follow-up visit.

- The **51-day efficacy period** which starts on the first day of IMP administration and ends at the end of treatment date.
 - This period will be composed of:
 - The **21-day on-treatment efficacy Period 1** which starts the day of first IMP intake during Period 1 and ends the earliest between end of Period 1 Day 21 date and permanent end of treatment date;
 - The on-treatment **wash-out period** which begins the day following the end of the 21-day on-treatment efficacy Period 1 and ends the day before the beginning of the 21-day on-treatment efficacy Period 2;
 - The **21-days on-treatment efficacy Period 2** which starts the day of IRT call for Period 2 and ends on the end of treatment date. This period is only defined for patients exposed to IMP during Period 2.
 - It will be used for efficacy analyses using the Full Analysis Set.
- The **51-day safety period** which starts on the first day of IMP administration and ends at the end of treatment date (+ x days).
 - This period will be composed of:
 - The **21 day on-treatment Safety Period 1** which starts the day of first IMP intake during Period 1 and ends the earliest between end of the wash out period date, the day before the date of IRT call for Period 2, the day before Visit 6 date and permanent end of treatment date + x days.
 - The **21 day on-treatment Safety Period 2** which starts the earliest between date of Visit 6, day of IRT on treatment safety period call for Period 2 date, and ends on the end of treatment day date + x days.
 - x will be equal to 14 days for Adverse events, 4 days for C-SSRS and 0 days otherwise.
 - it will be used for safety analyses using the Safety Analysis Set (unless otherwise specified).
- The **Follow-up period** which starts the day following the 51-day on-treatment safety period and ends on the end of study date.

10.1.2 Reference Day and Study Day

The reference day (Day 1) will be the day of the first dose of study drug administration.

For a patient who was randomized but not exposed, the reference day date will be imputed by the randomization date.

The reference day for Period 1 (Period 1 Day 1) will be the reference day.

The reference day for Period 2 (Period 2 Day 1) will be the first day of IMP administration during Period 2. For a patient who entered the second period but was not exposed during this period, this reference day date will be imputed by the date of Visit 6 IRT call, if any, or the Visit 6 date.

The study day is defined relative to the reference day date. For assessments that occur after this visit date, the study day is calculated as (assessment date – reference day date + 1). For assessments that occur prior to first dose date, study day will be calculated as (assessment date – reference day date).

For the analyses being done by treatment arm, an **analysis day** will need to be derived for each treatment period as described in Table 10.1-1. The analysis day is defined relative to the date of reference day of each study period.

For assessments that occur prior to reference day date, analysis day will be calculated as (assessment date – reference day date);

For assessments that occur on or after the Period 1 reference day date until the end of the wash-out period, analysis day will be calculated as (assessment date – Period 1 reference day date +1);

For assessments that occur on or after Period 2 reference day date the analysis day will be calculated as (assessment date – Period 2 reference day date +1);

Thus, there is no study day or analysis day referring to Day 0.

10.1.3 Target Days and Visit Window

Visit windows are summarized in [Table 10.1-3](#) for efficacy data and urine drug screen collection and, in [Table 10.1-2](#) for all other safety endpoints.

When there are multiple observations within a visit window, the value closest to the target day will be analyzed (as described in [Table 10.1-1](#)).

For safety assessments, on-treatment assessments will be preferred to off-treatment ones.

In case of ties between observations located on different sides of the target, the observation with the earliest date/time will be used. In case of ties between observations located on the same side of the target, (i.e., more than one value for the same day but at different time), the observation with the earliest date/time will be used. However, in case of non-respect of wash-out period, the one done at least 7 days after last Period 1 dosing date will be preferred.

For efficacy, PRO endpoints visit windowing will apply whether patient is on or off treatment.

Table 10.1-1 Longitudinal Assessment – Analysis Day and Target Day

Treatment Period	Visit / Day	Analysis visit	Target Day (defined by period)	Observation used for analysis, if more than one exists
Screening	Visit 1 / Day -28 to -1	Screening	Day -28 to -1	Latest value
Period 1	Visit 2 / Day 1	Day 1	Day 1*	Closest to Target Day But Day 1 H0 should be before 1 st IMP intake and Day 1 H3 should be post IMP intake
	Visit 3 / Day 8	Day 8	Day 8	Closest to Target Day
	Visit 4 / Day 15	Day 15	Day 15	Closest to Target Day
	Visit 5 / Day 21	Day 21	Day 21	Closest to Target Day
Period 2	Visit 6 / Day 31	Day 1	Day 1*	Closest to Target Day But Day 1 H0 should be before 1 st IMP intake and

				Day 1 H3 should be post IMP intake.
	Visit 7 / Day 38	Day 8	Day 8	Closest to Target Day
	Visit 8 / Day 45	Day 15	Day 15	Closest to Target Day
	Visit 9 / Day 51	Day 21	Day 21	Closest to Target Day
Follow-up	Visit 10 / Day 58	Day 28	Day 28**	Closest to Target Day

H = Hours; IMP = Investigational medical product.

** Day 1 is based on the date of IRT call within each period*

*** Day 28 relative to the period where IMP is permanently discontinued thus visit is expected between Day 25 and Day 31*

Table 10.1-2 Longitudinal Assessment – Target Day and Visit Window – Part 1

Treatment Period	Visit / Day	Physical examination / 12-lead ECG / Clinical laboratory blood sampling	Target Day (defined by period)	Examination of oral mucosa / C-SSRS	Body weight / Serum urine pregnancy test	Vital signs	Dipstick urine
Screening	Visit 1 / Day - 28 to -1	Day 28 – D1H0	Day 28 to -1	Day 28 to -1	Day 28 to -1	Day 28 to -1	Day 28 – D1H0 (before 1st IMP dosing)
Period 1	Visit 2 / Day 1H0	Day 1*	Day 1H0 *	Day 1H0 (before P1 IMP intake)	Day 1 H0 (before P1 IMP intake)	Day 1 H0 (before P1 IMP intake)	Day 1 post dose (the day of 1st P1 IMP intake)
	Visit 2 / Day 1	Day 1 H2- H4*					Day 2 (day following IMP intake) – Day 18
	Visit 4 / Day 15	Day 15		Day 1 post dose to Day 18			Day 19 to LP1V
	Visit 5 / Day 21	Day 21	Day 1 post dose to LP1V	Day 19 to LP1V			
	Wash-out						
Period 2	Visit 6 / Day - 31	Day 1H0*		Day 1 – 4 days to D1H0 *	D1H0 (before P2 IMP intake)	Day 1 – 4 days to D1H0	Day 1 post dose (the day of 1st P2 IMP intake)
	Visit 6 / Day - 31	Day 1H2- H4*					Day 2 (day following IMP intake) – Day 18
	Visit 8 / Day 45	Day 15		Day 1 post dose to Day 18			Day 19 to LP2V
	Visit 9 / Day 51	Day 21	Day 1 post dose to LP2V	Day 19 to LP2V			
	Follow-up	Visit 10 / Day 58	Day 28***		after last IMP dosing	After last IMP dosing	Day 1 post 1st IMP dosing to after last IMP dosing

H = Hour; P = Period; LP1V = Last visit during Period 1, LP2V = Last visit during Period 2, IMP = Investigational Medical Product; IRT = Interactive response technology; ECG = Electrocardiogram; C-SSRS = Columbia-Suicide Severity Rating Scale.

** Day 1 is based on the date of IRT call within each period.*

**** Day 28 relative to the period where IMP is permanently discontinued.*

Table 10.1-3 Longitudinal Assessment – Target Day and Visit Window – Part 2

Treatment Period	Visit / Day	Target Day (defined by period)	Urine drug screen	11-point NRS spasticity / Daily spasm count	MAS	MSSS-88	T25FW test
Screening	Visit 1 / Day - 28 to -01	Day -28 to -01	Day -28 to -01	Day -28 to -01	Day -28 to -01		
Period 1	Visit 2 / Day 1H0	Day 1*	Day 1 H0 (before P1 IMP intake)	Day1H0 (before P1 IMP intake)*	Day1H0 (before P1 IMP intake)	Day 1H0 (before P1 IMP intake)	Day 1H0 (before P1 IMP intake)
	Visit 2 / Day 1	Day 1 H2- H4**			Day1 post dose (the day of 1 st P1 IMP intake)** up to Day 18		
	Visit 4 / Day 15	Day 15		Day 2 (day following IMP intake) – Day 18 (or the first day of maintenance phase)			
	Visit 5 / Day 21	Day 21***		Day 19 up to LP1V	Day 19 up to LP1V	Day 1 post dose of 1 st IMP intake up to LP1V	Day 1 post dose of 1 st IMP intake up to LP1V
Wash out period							
Period 2	Visit 6 / Day 31	Day 1H0*		Day 1 – 4 days to D1H0 *	Day 1H0 (before P2 IMP intake)	Day 1H0 (before P2 IMP intake)	Day 1H0 (before P2 IMP intake)
	Visit 6 / Day 31	Day 1H2- H4**			Day 1 post dose (the day of 1 st P2 IMP intake)** up to Day 18		
	Visit 8 / Day 45	Day 15		Day 2 (day following IMP intake) – Day 18 (or the first day of maintenance phase)			
	Visit 9 / Day 51	Day 21***		Day 19 to LP2V	Day 19 to LP2V	Day 1 post dose of Period 2 1 st IMP intake up to LP2V	Day 1 post dose of Period 2 1 st IMP intake up to LP2V
Follow-up	Visit 10 / Day 58	Day 28****		After last IMP dosing			

H = Hours, P = Period; LP1V = Last visit during Period 1, LP2V = Last visit during Period 2, IMP = Investigational Medicinal Product, NRS = Numerical Rating Scale; IRT = Interactive Response System, MAS = Modified Ashworth Scale, MSSS-88 = Multiple Sclerosis Spasticity Scale; T25FW = Timed 25-Foot Walk.

* Day 1 is based on the date of IRT call within each period.

** D1H2-H4 for sensitivity analysis purpose only assessments collected between at H3 (+/- 15 min) post first IMP morning spray will be considered. Should be collected during the titration phase

*** Day 21 should be collected during the maintenance phase (including off-treatment days).
 **** Day 28 relative to the period where IMP is permanently discontinued.

